Adaptation of Mindfulness Training to Treat Moral Injury in Veterans

May 22, 2023

NCT Number: NCT05341882

Statistical Design and Power

The goal of the proposed R34 is to adapt the MMCP program for combat wounded veterans with moral injury and compare its acceptability, adherence, and implementation/practicality to an equally intensive online, facilitator-led, interactive education support group comparison condition. We will also collect data to identify potential primary and second outcome measures for a future sufficiently powered RCT.

Design

Aim 1: Adapt MMCP to Address Moral Injury (Study 1)

Study 1 is designed to adapt an existing mindfulness program to be appropriate for moral injury via an iterative developmental process based on existing literature and our previous research. For instance, we will make some key modifications to the mindfulness content to be appropriate for those with moral injury, including a self-compassion/loving kindness exercise based on previous research.¹⁴⁹ We will also obtain information and feedback from stakeholders (veterans, mental health providers). To achieve this objective, the PI and co-Is will have monthly meetings to develop and adapt the program content. We will ask for feedback from moral injury researchers and providers including members of APA's Division 19 Moral Injury Think Tank (chaired by the PI) for which they will receive small renumeration.

As part of Study 1, [name] (consultant/interventionist) will provide the six 75-minute weekly audiotaped MMMI program sessions to six eligible participants. Upon completion of the MMMI program, semi-structured interviews will be conducted utilizing a post-positivist paradigm,¹⁵⁰ guided by awareness that combat wounded veterans are a diverse population, have different experiences with moral injury, and may have different program reactions. All interviews will be conducted by the PI and GRA. The GRA and graduate and undergraduate lab members (many of whom are student veterans given the PI's focus on veteran mental health and the large student veteran population at the PI's university in Norfolk, VA), will transcript videotapes and develop initial coding themes. These themes will be reviewed by the research team and lead to MMMI refinement and preliminary manualization.

Aim 2: Examine the Intervention's Feasibility, Acceptability, and Preliminary Efficacy (Study 2)

In Study 2, we propose to test our ability to recruit and retain participants, to implement the designed protocol, and to determine treatment adherence of the refined MMMI intervention as compared to a facilitator-led ES comparison group ($N = 20$ combat wounded veterans; 10 MMMI; 10 ES). The two groups (MMMI and ES) will not differ in the delivery (i.e., live facilitator led interactive web-based, number of sessions, length of sessions, and have manualized treatments). Further, some content will be identical (e.g., introductions, icebreakers) or similar (e.g., benchmarks, semi-structured interview). We will gather audiotaped semi-structured interviews and brief benchmark measures to assess the feasibility, acceptability, participant comments and suggestions, as well as and participant acceptance, satisfaction, and compliance data. See Table 1.

Because there is no treatment-as-usual comparable to MMMI, several factors guided our decisions in developing the control group. In a different patient population, co-I [name] developed and compared an ES group to a mindfulness training group. Although the mindfulness group developed specific mindfulness skills, the two groups did not differ in their ratings of the credibility of their assigned interventions.¹⁴² Also, an active control condition provides a stronger study design.¹⁵¹ Third, treatment of the control condition should only differ from the experimental condition in the 'non-receipt' of the 'active ingredient'.¹⁵² Also, 59% of veterans who took part in a Wounded Warrior Project survey reported talking with other veterans "as a top resource for coping with stress".¹⁵³ Finally, researchers have provided moral injury treatment in weekly group meetings.^{65,99}

Aim 3. To Evaluate the Preliminary Feasibility of the Interventions (Study 3)

In Study 3, we propose to test the refined interventions with a larger group of combat wounded veterans ($N = 60$ combat wounded veterans; 30 MMMI; 30 ES group). After completing the baseline measures, participants will be randomly assigned to program. We will collect information on acceptability, adherence, and implementation/practicality in the two intervention arms, as well as primary moral injury symptoms (e.g., guilt, shame), possible mechanisms of changes (e.g., acceptance, nonjudgment, compassion), and possible secondary outcomes (e.g., mental health symptoms, substance use), which will help inform key variables to include in a large-scale sufficiently powered RCT. See Table 3.

Sample Size Determination

Prior to determining the sample size for Study 3, we examined the literature on determination of sample size for feasibility studies.¹⁵⁵⁻¹⁵⁷ We specifically examined prior eligibility, refusal, randomization and session and data completion rates. We also considered practical aspects such as eligibility criteria, refusal and dropout rates,

expected interview and data completion rates, therapist hours and length of training, supervision, fidelity coding, and timeline. Overall, the majority of feasibility studies had modest sample sizes with varying rates of participation completion: 57% (n = 21),¹⁰⁷ 81% (n = 33),⁹⁷ and 77% (n = 37).¹¹⁰ Based on averages from previous studies,^{97,107,110} we will recruit 60 combat wounded veterans. Furthermore, we expect an ineligible rate/refusal rate of 30% (n = 18) and that an additional 18.8% (n = 8) will attend no sessions and/or not complete the post-training semi-structured interview or other survey measures, for a conservative completion rate of 34 participants. Given that the MMMI and ES support group will be equal in delivery, facilitation, group size, length, home practice burden, we do not anticipate different group completion rates.

Aim 2: Examine the Intervention's Feasibility, Acceptability, and Preliminary Efficacy (Study 2)

In Study 2, we propose to test our ability to recruit and retain participants, to implement the designed protocol, and to determine treatment adherence of the refined MMMI intervention as compared to a facilitator-led ES comparison group (N = 20 combat wounded veterans; 10 MMMI; 10 ES). The two groups (MMMI and ES) will not differ in the delivery (i.e., live facilitator led interactive web-based, number of sessions, length of sessions, and have manualized treatments). Further, some content will be identical (e.g., introductions, icebreakers) or similar (e.g., benchmarks, semi-structured interview). We will gather audiotaped semi-structured interviews and brief benchmark measures to assess the feasibility, acceptability, participant comments and suggestions, as well as and participant acceptance, satisfaction, and compliance data. See Table 1.

Because there is treatment-as-usual comparable to MMMI, treatment-as-usual comparable to MMMI, several factors guided our decisions in developing the control group. In a different patient population, co-I [name] developed and compared an ES group to a mindfulness training group. Although the mindfulness group developed specific mindfulness skills, the two groups did not differ in their ratings of the credibility of their assigned interventions.¹⁴² Also, an active control condition provides a stronger study design.¹⁵¹ Third, treatment of the control condition should only differ from the experimental condition in the 'non-receipt' of the 'active ingredient'.¹⁵² Also, 59% of veterans who took part in a Wounded Warrior Project survey reported talking with other veterans "as a top resource for coping with stress".¹⁵³ Finally, researchers have provided moral injury treatment in weekly group meetings.^{65,99}

Table 1. Measurable Benchmarks Administered during Study 2 and 3

Area of Interest	Description of Outcome to be Evaluated	Measure and/or Expected Outcome
Acceptability	Participant Satisfaction	Client Satisfaction Questionnaire (CSQ-8) ¹⁵⁴ satisfaction of $\geq 80\%$
	Intention to continue to use skills	Questionnaire developed for this study
	Training appropriateness	Questionnaire developed for this study
Demand	Completed sessions	$\sim 52\%$ of those who meet eligibility criteria will attend 4 to 6 sessions based on previous studies ^{97,107,110}
	Homework Practice	Gradual increase in minutes of home practice relative to the number of minutes assigned over the 6 weeks $\sim 40\%$ of those who attend 4 to 6 sessions will complete 80% or more homework
Implementation/ Practicality	Screening/eligibility for study/ dropout	Record number of call attempts for each participant and reasons for ineligibility/decision not to participate/dropout
	Recruitment	Recruit, phone screen, and explain study to eligible participants for Study 1 within 2 weeks, Study 2 within 1 month, and Study 3 within 2 months. Obtained signed informed consent from participant.
	Retention	Among those randomized, 34/42 (81%) will attend 1 or more sessions ^{97,107,110}
	Assessment completion	For assessments attempted, 90% completion rate

Aim 3. To Evaluate the Preliminary Feasibility of the Interventions (Study 3)

In Study 3, we propose to test the refined interventions with a larger group of combat wounded veterans (N = 60 combat wounded veterans; 30 MMMI; 30 ES group). After completing the baseline measures, participants will be randomly assigned to program. We will collect information on acceptability, adherence, and implementation/practicality in the two intervention arms, as well as primary moral injury symptoms (e.g., guilt, shame), possible mechanisms of changes (e.g., acceptance, nonjudgment, compassion), and possible

secondary outcomes (e.g., mental health symptoms, substance use), which will help inform key variables to include in a large-scale sufficiently powered RCT. See Table 3.

Sample Size Determination

Prior to determining the sample size for Study 3, we examined the literature on determination of sample size for feasibility studies.¹⁵⁴⁻¹⁵⁶ We specifically examined prior eligibility, refusal, randomization and session and data completion rates. We also considered practical aspects such as eligibility criteria, refusal and dropout rates, expected interview and data completion rates, therapist hours and length of training, supervision, fidelity coding, and timeline. Overall, the majority of feasibility studies had modest sample sizes with varying rates of participation completion: 57% (n = 21),¹⁰⁷ 81% (n = 33),⁹⁷ and 77% (n = 37).¹¹⁰ Based on averages from previous studies,^{97,107,110} we will recruit 60 combat wounded veterans. Furthermore, we expect an ineligible rate/refusal rate of 30% (n = 18) and that an additional 18.8% (n = 8) will attend no sessions and/or not complete the post-training semi-structured interview or other survey measures, for a conservative completion rate of 34 participants. Given that the MMMI and ES support group will be equal in delivery, facilitation, group size, length, home practice burden, we do not anticipate different group completion rates.

Aim 2 and 3: Examining the Intervention's Fidelity, Feasibility and Acceptability

Maintenance and Evaluation of Treatment Fidelity. We will provide ongoing assessment of treatment fidelity among facilitators following recommendations made by Borrelli¹⁷⁴. Specifically, facilitators will utilize a treatment manual that will detail session-specific components and proscribed topics, along with a checklist to ensure completion. Contact minutes per group will be recorded to ensure duration consistency across groups. Deviations from protocol will be recorded by the facilitators. Further, all sessions will be audio-recorded via state-of-the-art Intelligent Video Solutions equipment (see Equipment). [name] or [name] will listen to at least one session per cohort group to ensure adherence to the manual across time and sessions. If either facilitator falls below a predetermined performance criterion or self-reported checklist indices, two sessions per group for that facilitator will be observed until adherence meets established criteria. Facilitators will be provided feedback during weekly supervision.

Evaluation of Feasibility and Acceptability. To evaluate feasibility and acceptability, we will rely on benchmarks proposed in the extant pilot/feasibility study literature.¹⁷⁶⁻¹⁷⁸ Specifically, we will assess methodological- (screening, recruitment, randomization, retention) and intervention- (treatment adherence) related components of the proposed protocol. Throughout recruitment and administration, we will assess for: (1) the number of veterans screened per week, (2) the number of veterans enrolled per week, (3) the proportion of screened participants who take part in the sessions, (4) the ability to randomize enrolled veterans, (5) the number of battery assessments completed, and (6) the proportion of questionnaires completed. Low rates could indicate a high level of perceived burden, limiting the feasibility of this intervention.

Specific to treatment components, we will: (1) assess the number of sessions completed by participants in each group, (2) assess the percent of completed mindfulness home practice assignments among intervention participants as compared to the home assignments from the ES group, and (3) compare the retention rate of participants assigned to the MMMI group to that of participants assigned to the ES control condition. High retention and homework completion rates will indicate that participants found the intervention acceptable and that, similar to the MMCP program (Brintz et al., in press), six sessions are acceptable. Based on prior studies conducted we anticipate 81% of those who meet study criteria and agree to participate will attend 4 to 6 sessions and complete the post-training semi-structured interview or other survey measures. Forty (40%) of those who attend 4 to 6 sessions will complete 80% or more homework, ~40% who attend 4 to 6 sessions will complete 40% to 80% of homework, and ~20% who attend 4 to 6 sessions will complete less than 40% of the homework. Acceptability will also be evaluated with the Client Satisfaction Questionnaire ($\geq 80\%$) and via two questionnaires developed for this study: (1) whether individuals intend to continue using the skills learned in the future, and (2) appropriateness of the intervention to treat moral injury.

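### Expected completion of 34 of 42 (81%) matches the highest of the three cited completion rates, whose average is about 72%, and the 18.8% loss behind it is not derived

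*Combined protocol and SAP*

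**What the plan says.** Sample Size Determination, which appears twice with the same figures, reports the precedents as "varying rates of participation completion: 57% (n = 21),¹⁰⁷ 81% (n = 33),⁹⁷ and 77% (n = 37).¹¹⁰". It continues: "Based on averages from previous studies,^{97,107,110} we will recruit 60 combat wounded veterans". The losses come next: "we expect an ineligible rate/refusal rate of 30% (n = 18"), and then "an additional 18.8% (n = 8) will attend no sessions and/or not complete the post-training semi-structured interview or other survey measures". The result is described with the words "for a conservative completion rate of 34 participants".

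The 81% implied by 34 of 42 appears in two more places, attached to different events:

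- Table 1, Retention row, citing the same three references: "Among those randomized, 34/42 (81%) will attend 1 or more sessions".
- Evaluation of Feasibility and Acceptability (under Aim 2 and 3): 81% of those who qualify and agree to take part are expected to attend four to six sessions and complete post-training measures. The stated basis is prior studies.

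**The concern.** An expectation said to rest on earlier studies should sit near the middle of what those studies showed, unless a reason is given for expecting better. Here it sits at the top of the listed range. The loss rate that produces it, 18.8%, appears without a source. The chain from 60 to 34 adds up, so checking the subtraction does not reveal the problem, which lies in the input.

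Feasibility is the main output of this study and is meant to inform a larger trial. The plan also says it will read high retention as a sign of acceptability. If the expectation is too favourable, the number of veterans with post-training data is overstated. A programme that completes participants about as well as its precedents would then look as though it had fallen short.

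**Working it through.** **Inputs.** From Sample Size Determination: 60 recruited; 30% ineligible or refusing; 18.8% further loss; precedent rates of 57% (n = 21), 81% (n = 33) and 77% (n = 37). From Table 1: 42 as the number randomised. The plan does not say whether each n counts completers or enrolled participants, nor what denominator each rate uses.

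**1. The plan's own figure.**
- 60 × (1 − 0.30) = 42.
- 42 × 0.188 = 7.9, rounded to 8.
- 42 − 8 = 34, and 34/42 = 81.0%. The stated figure reproduces.
- Against all those recruited, 34/60 = 56.7%.

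**2. Average of the three precedents.**
- Unweighted: (57 + 81 + 77)/3 = 71.7%.
- If n is the number enrolled: (0.57 × 21 + 0.81 × 33 + 0.77 × 37)/91 = 67.19/91 = 73.8%.
- If n is the number completing: 91/(21/0.57 + 33/0.81 + 37/0.77) = 91/125.6 = 72.4%. With whole-number denominators, 91/(37 + 41 + 48) = 72.2%.

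The completer reading fits the figures better (21/37 = 56.8%, 37/48 = 77.1%, 33/41 = 80.5%), but that is an inference. An average that gives any weight to the other two studies must fall below 81%. The implied loss is 26% to 28%, against the plan's 18.8%.

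**3. Expected completers out of 42**, taking the precedent rates as per enrolled participant.
- At the average: 42 × 0.717 = 30.1, rising to 42 × 0.738 = 31.0.
- At the lowest and highest precedent: 42 × 0.57 = 23.9 and 42 × 0.81 = 34.0, so 24 to 34.

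**4. Chance of at least 34 of 42**, exact binomial, P(X ≥ 34) with n = 42.

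| True completion rate | P(X ≥ 34) |
|---|---|
| 57% | 0.001 |
| 71.7% | 0.12 |
| 72.2% to 72.4% | 0.14 |
| 73.8% | 0.19 |
| 77% | 0.35 |
| 81% | 0.60 |

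A true rate of about 79.5% is needed for an even chance.

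**The case against.** Several points on the other side are sound, and they limit what can be claimed.

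- **A reader might infer that the plan calls 81% an average.** It does not. The reference to averages is attached to recruiting 60, and the loss rates follow in a new sentence. Table 1 only cites the three studies beside 81%, and the evaluation text says prior studies. What stands is that 81% is presented as precedent-based without disclosing that it is the best of the three.
- **A reader might infer that the word conservative is simply wrong.** It qualifies 34, reached after both losses from 60. As 56.7% of those recruited, 34 matches the lowest precedent, so the label can be defended on that denominator. That reading has its own difficulty: after a 30% loss at entry the plan cannot exceed 42/60 = 70% of those recruited, so precedents of 77% and 81% per person recruited would lie above its own ceiling.
- **A reader might infer that the Table 1 retention benchmark would probably be missed.** That item counts attendance at one or more sessions, which is easier than completion. A trial that matched its precedents on completion could exceed 81% on it, so the 12% to 19% does not carry over.
- **The three studies may hold other relevant rates.** Table 1 also cites them for about 52% attending four to six sessions, which is not the average of the listed rates either. This cannot be excluded, but the plan shows no such derivation for 81%.
- **No go/no-go rule depends on 34 of 42.** This is true. Nor is the 0.60 at a true rate of 81% a fault: a benchmark set at its expected value is met only a little more than half the time.

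**Conclusion.** The concern holds for the completion figures in both Sample Size Determination sections and in Evaluation of Feasibility and Acceptability. There the event is close to the precedents' completion, and 81% is the highest of the three listed rates, about 7 to 9 percentage points above their average. The expected number is overstated by about three or four participants out of 42 (34 against 30 to 31), and 34 would be reached in roughly one trial in five to one in eight.

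These sizes assume that the precedent rates are per enrolled participant, that 42 are randomised, and that participants complete independently at a common rate. Delivery in groups makes the last assumption approximate. The documents do not establish that the Table 1 retention item is miscalibrated for its own event, only that its link to the cited rates is not shown. This is a correctable weakness in a planning figure that the feasibility evaluation relies on, and it does not invalidate the design.

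**What to change.** 1. In both Sample Size Determination sections and in Evaluation of Feasibility and Acceptability, restate expected completion as about 72%, or about 30 of 42, with a range of 57% to 81% (24 to 34). Alternatively, keep 81% and label it a target equal to the best precedent.
2. State the denominator and the event behind each of the three precedent rates, and show how 18.8% was obtained.
3. Remove the word conservative, or say that it refers to 34 of the 60 recruited (57%).
4. In Table 1, do not put 72% on the item for one or more sessions. Either base that benchmark on precedent rates for that same event, or redefine the item as completion and use the restated figure.

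The cost is wording and one recalculated figure. Enrolment does not change. The downside is a less favourable expected number of completers, about 30 instead of 34.

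### The Table 1 benchmark for attending 4 to 6 sessions counts eligible veterans who decline, so it mixes uptake with adherence, and it does not agree with the 81% given elsewhere for the same attendance

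*Combined protocol and SAP*

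**What the plan says.** Four places bear on attendance.

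- **Table 1, Demand, completed sessions** (Studies 2 and 3): about 52% "of those who meet eligibility criteria will attend 4 to 6 sessions based on previous studies".
- **Table 1, Implementation/Practicality, retention:** "Among those randomized, 34/42 (81%) will attend 1 or more sessions".
- **Evaluation of Feasibility and Acceptability:** "we anticipate 81% of those who meet study criteria and agree to participate will attend 4 to 6 sessions" and also provide the post-training interview or other survey data. The same section plans to count sessions completed in each group and to compare retention between MMMI and ES.
- **Sample Size Determination** (Study 3): "we will recruit 60 combat wounded veterans". Of these, 30% (18) are expected to be ineligible or to refuse, given as one pooled figure. Then "an additional 18.8% (n = 8) will attend no sessions and/or not complete the post-training semi-structured interview or other survey measures". The plan takes this to leave 34 who complete.

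Under Aim 3, Study 3 has 30 veterans per arm, randomised after the baseline measures, and the plan says "We will collect information on acceptability, adherence, and implementation/practicality in the two intervention arms". Table 1 also requires reasons for ineligibility, for deciding not to take part and for dropout to be recorded.

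**The concern.** The three attendance statements use three bases: those eligible, those eligible who agree, and those randomised. Because the feasibility section adds agreement as a further condition, and Table 1 lists ineligibility and the decision not to take part as separate reasons, the plan itself treats eligibility and agreement as different steps. On its plain wording, then, the 52% row counts an eligible veteran who declines as someone who did not attend 4 to 6 sessions.

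Two things follow. Refusals before randomisation move the result although they say nothing about how assigned veterans took to MMMI or ES. And the 52% cannot be applied to each arm, although acceptability and adherence are to be described by arm. In addition, 52% and 81% are both offered as the expectation for 4 to 6 sessions. A team planning the later trial would not know which one the observed attendance should be compared with.

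**Working it through.** **Inputs.** From Sample Size Determination: 60 recruited, 30% (18) ineligible or refusing, a further 18.8% (8) lost, 34 completing. From Table 1: about 52% of the eligible attend 4 to 6 sessions; 34/42 (81%) of the randomised attend at least one. From Evaluation of Feasibility and Acceptability: 81% of those eligible and agreeing attend 4 to 6 sessions and give post-training data.

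**Step 1. Reproduce the plan's flow.** 60 × 0.70 = 42. 42 × (1 − 0.188) = 34.1, so 34. 34/42 = 81.0%. The flow reproduces; 8/42 is 19.0% against the stated 18.8%, a gap of rounding size.

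**Step 2. Try to reproduce the 52%.** No numerator or derivation is given. Several routes come close:

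- 22/42 = 52.4%.
- 31/60 = 51.7%.
- The mean of the three cited completion rates, weighted by the n printed beside each, times 0.70: (0.57 × 21 + 0.81 × 33 + 0.77 × 37)/91 = 73.8%, and 73.8% × 0.70 = 51.7%.
- The simple mean of those rates times 0.70: 71.7% × 0.70 = 50.2%.

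The figure fits a base of 42 and a base of 60 about equally well, so it cannot be tied to either.

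**Step 3. Effect of the denominator.** Assumption: R of the 18 pooled losses are eligible refusers. The plan gives no split, so R runs from 0 to 18. The eligible number is 42 + R, and the attendance needed is 0.52 × (42 + R).

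| R | Eligible | Attenders needed | As share of 42 randomised |
|---|---|---|---|
| 0 | 42 | 21.8 | 52.0% |
| 9 | 51 | 26.5 | 63.1% |
| 18 | 60 | 31.2 | 74.3% |

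Illustration away from the extremes: suppose 24 of the 42 randomised attend 4 to 6 sessions (57.1%). With R = 4 the rate is 24/46 = 52.2%; with R = 5 it is 24/47 = 51.1%. One more refusal carries the result across 52% with no change among the randomised.

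**Step 4. Can refusal reconcile 52% with 81%?** Take those eligible and agreeing to be the same 42 (no loss between agreement and randomisation). Then 81% is 34 veterans. Since the 81% also requires post-training data, 34 is the least number attending 4 to 6 sessions that it implies. Spread over the largest possible eligible group, 34/60 = 56.7%. Getting down to 52% needs 34/0.52 = 65.4 eligible veterans, more than the 60 recruited. Refusal alone does not close the gap. On the base of 42, the two figures are about 22 and 34 attenders, a difference of 12.

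**Step 5. Does it matter whether 42 or 60 are randomised?** The retention row takes 42 as randomised; the design gives 30 + 30. The proportions depend only on the 30% pooled loss: 0.52/0.70 = 74.3% and 0.81 × 0.70 = 56.7%. The range in Step 3 and the conclusion in Step 4 are therefore unchanged if 60 are randomised and the 30% is lost before that. Only the counts change.

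**The case against.** The row sits under Demand, and counting eligible people who decline is a reasonable measure of demand; retention is a separate row with a randomised base. Refusal reasons are logged, the number of eligible veterans will be known when the rate is calculated, and sessions completed are planned by group. Most of this stands. It limits the point to the benchmark, but it does not remove it: the row is about sessions completed, the same attendance threshold has a second expectation on another base, and the two disagree by more than refusal can account for.

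A reader might infer more than the documents support:

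- *That adherence by arm will not be assessed.* It will be. The feasibility section plans sessions completed in each group and a retention comparison. Only the 52% lacks a by-arm form.
- *That attendance of 74% among the randomised is what the plan demands.* That is the boundary case in which all 18 losses are eligible refusers. The documents give no split, and 22/42 also fits, so the authors may have meant the 42.
- *That missing 52% has a consequence.* The column lists measures or expected outcomes, the figure is approximate, and no progression rule is attached to it.
- *That 52% can simply be moved to the randomised, giving 22 of 42 or 11 per arm.* Its origin is not stated, the feasibility section expects about 34 of 42 for the same attendance, and the design gives 30 per arm. If 52% was set on a base including refusers, carrying it over would lower the bar.

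**Conclusion.** The point holds as a defect in how one benchmark is defined and in its agreement with the rest of the plan. As worded, the Table 1 attendance figure mixes uptake with adherence and cannot be used by arm. Its meaning among the 42 randomised ranges from 52% to 74%, depending only on an unstated split of the 18 pooled losses. It also conflicts with the 81% in the feasibility section, and that conflict remains under every split (56.7% at the least). The 81% is itself attached to at least one session in one place and to 4 to 6 sessions in another.

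These results rest on the literal reading of the eligibility wording, on the 30% pooled loss, and on treating those who agree as those randomised. They do not show which of 52% and 81% the authors intended. The importance is moderate: no decision rule hangs on the figure, but attendance by arm is among the main things this feasibility work is meant to pass on to the later trial.

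**What to change.** 1. State one benchmark for attending 4 to 6 sessions, over randomised veterans, overall and by arm, and use it both in Table 1 and in Evaluation of Feasibility and Acceptability.
2. Re-derive the percentage for that base and show the derivation. Do not carry 52% over unchanged.
3. Report uptake (randomised divided by eligible) as a separate rate. The reasons for ineligibility and for declining are already to be recorded. Giving an expected split of the 18 would help but is not essential.
4. Say whether 81% refers to at least one session or to 4 to 6 sessions, and whether it requires post-training data.
5. Say whether 42 or 30 + 30 are to be randomised in Study 3, and state the base that applies in Study 2 (10 + 10), since Table 1 covers both studies.

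The cost is wording in Table 1, the feasibility section and the sample-size paragraph. No new data are needed. The downside is that the re-derived benchmark may differ from the one now stated, so it should be fixed before attendance data are examined.

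### Expected attendance at 4 to 6 sessions is stated as about 52% in one place and 81% in another, and 81% is attached to different outcomes, so 'retention' has no single meaning

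*Combined protocol and SAP*

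**What the plan says.** Four places in the combined protocol and SAP bear on this point.

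- **Table 1, Demand, Completed sessions.** About 52% "of those who meet eligibility criteria will attend 4 to 6 sessions based on previous studies".
- **Table 1, Implementation/Practicality, Retention.** "Among those randomized, 34/42 (81%) will attend 1 or more sessions".
- **Sample Size Determination** (printed twice with the same figures). Of 60 recruited, "we expect an ineligible rate/refusal rate of 30% (n = 18"). Another 8 people (18.8%) are then removed, described as those who "will attend no sessions and/or not complete the post-training semi-structured interview or other survey measures". The count closes with the words "for a conservative completion rate of 34 participants".
- **Evaluation of Feasibility and Acceptability.** "we anticipate 81% of those who meet study criteria and agree to participate will attend 4 to 6 sessions" and also complete the interview or surveys. The sentence just before this reads "High retention and homework completion rates will indicate that participants found the intervention acceptable" and goes on to say that, as in the parent programme, "six sessions are acceptable".

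That last section also plans to count sessions completed in each group, to compare homework completion between groups and to compare the retention rate between arms. Table 1 has a separate row for assessment completion and plans to record reasons for dropout.

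**The concern.** Two expected values are given for what looks like the same outcome, attendance at 4 to 6 sessions. The figure of 81% is also used, directly or by implication, for three outcomes of increasing strictness: attending at least once; attending and completing the post-training measures; and attending 4 to 6 sessions and completing the interview or surveys.

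Acceptability, adherence and practicality are the main product of this trial. A report that the 81% benchmark was met would not tell the reader whether participants started, stayed for most of the programme, or completed the assessments. Each would lead to a different plan for the later powered trial. The plan also takes high retention, with homework completion, as evidence about six sessions, so the meaning of 'retention' affects a stated conclusion as well as a table label.

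**Working it through.** **Inputs.** From Sample Size Determination: 60 recruited, 30% (18) ineligible or refusing, 18.8% (8) lost after that, 34 completers. From Table 1: 34/42 (81%) attending at least once, and about 52% of those eligible attending 4 to 6 sessions. From Evaluation of Feasibility and Acceptability: 81% of those who meet criteria and agree attend 4 to 6 sessions and complete the interview or surveys.

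**The plan's own figure.** 60 × 0.30 = 18; 60 − 18 = 42; 42 × 0.188 = 7.9, so 8; 42 − 8 = 34; 34/42 = 81.0%. It reproduces.

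**The three uses of 81% side by side.** On a base of 42, all three outcomes can equal 34 only if nobody stops after 1 to 3 sessions and no attender misses the post-training measures.

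**The two 4-to-6-session figures.** Let E be the number who meet eligibility criteria. The 18 losses are not split into ineligible and refused, so E runs from 42 (all 18 ineligible) to 60 (all 18 refused). In either case 42 meet criteria and agree, and 0.81 × 42 = 34.0.

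| E | 0.52 × E | 81% of 42 | Gap (people) | 34/E |
|---|---|---|---|---|
| 42 | 21.8 (22) | 34 | 12 | 81.0% |
| 48 | 25.0 (25) | 34 | 9 | 70.8% |
| 54 | 28.1 (28) | 34 | 6 | 63.0% |
| 60 | 31.2 (31) | 34 | 3 | 56.7% |

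Exact agreement needs E = 34/0.52 = 65.4, above the 60 recruited. As a share of the 42, the Table 1 figure is 22/42 = 52.4% to 31/42 = 73.8%, against 81%.

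**What a one-session retention rate leaves out.** Table 1's two rows are compatible with each other, because those attending 4 to 6 sessions are a subset of those attending at least one. Taken together, they imply that 34 − 31 = 3 to 34 − 22 = 12 of the 34 starters (3/34 = 9% to 12/34 = 35%) do not reach a fourth session while Retention still reads 81%.

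**Whether homework fills the gap.** The homework benchmark (about 40% completing 80% or more) is set among those who attend 4 to 6 sessions. It is conditional on getting that far, so it cannot show how many did.

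**Precision per arm** (exact Clopper-Pearson 95% intervals). If 42 are split evenly, 11/21 = 52.4% has an interval of 29.8% to 74.3%. With the stated 30 per arm, 16/30 = 53.3% has an interval of 34.3% to 71.7%.

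**The case against.** Four points can fairly be made for the plan.

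1. **Different denominators.** A reader might infer a like-for-like conflict of 81% against 52%, or 29 percentage points. The documents do not support that. One rate is among those eligible, the other among those eligible who also agree. If all 18 losses were refusals, the comparison narrows to 56.7% against an approximate 52%, which might pass as rounding. But that end requires that none of the 60 be ineligible, while the plan itself names ineligibility as part of the 30%. Every ineligible person widens the gap.

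2. **Retention may not mean one session in the six-session inference.** A reader might infer that the plan will call six sessions acceptable because people attended once. The text does not establish this. The inference sentence is followed at once by the 81% expectation for 4 to 6 sessions plus assessment, and then by the homework percentages. The natural reading is that retention there means the stricter outcome. This objection largely stands. What remains is that Table 1 attaches the word to attending once, and nothing says which meaning applies.

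3. **Retention is not the only evidence.** Homework completion is also required, session counts are planned by group, and dropout reasons are recorded. A reader might infer that heavy dropout would be hidden. It would not be; it would show descriptively. However, no text ties the session counts to the six-session conclusion.

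4. **The 81% may not be one figure reused.** Only Table 1 writes 34/42. Sample Size Determination gives 18.8% and 34, and also cites a completion rate of 81% (n = 33) from an earlier study, which may be the source of the later 81%. This stands. The origin is unknown, but the same percentage is still attached to different outcomes.

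**Conclusion.** The expected rate of attending 4 to 6 sessions is stated inconsistently. The gap is about 3 to 12 people out of 34, depending on how the 18 losses divide, and no eligible count from 42 to 60 removes it. The term 'retention' is ambiguous between attending once (Table 1) and, apparently, attending 4 to 6 sessions and completing assessments (Evaluation of Feasibility and Acceptability). Only on the Table 1 meaning would the retention part of the six-session inference fail to measure staying in treatment.

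The counts assume that all 42 are randomised and that nobody who refuses attends. The plan elsewhere assigns 30 to each arm, 60 in all, so the randomised denominator itself needs stating. The benchmarks are expectations with no stated go/no-go threshold. The harm is therefore an uninterpretable feasibility result rather than a wrong decision rule. The point should be corrected before results are reported; it does not undermine the data collection.

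**What to change.** - For each of three outcomes (attendance at 1 or more sessions, attendance at 4 to 6 sessions, completion of the post-training assessment), state one expected rate and one denominator. Make Table 1, both copies of Sample Size Determination, and Evaluation of Feasibility and Acceptability agree. Give the expected split of the 18 into ineligible and refused.
- Use 'retention' for only one of the three. Which one is a matter of choice.
- Base the six-session conclusion on 4-to-6-session attendance among all randomised to MMMI, and the between-arm comparison on the same outcome among all randomised, reported by arm. Show the planned session counts alongside, since someone who leaves after session 4 still counts as attending 4 to 6.

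**Cost.** Wording changes and one by-arm table from data already planned. The headline figure may be less favourable than 81%, and per-arm precision is poor: about 30% to 74% for 11/21, or 34% to 72% for 16/30. The comparison with the expected rate can only be descriptive.
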